6.5.2 FOLLOW-UP OF POST TRIAL SERIOUS ADVERSE EVENTS

SAEs that are identified on the last scheduled contact (or early discontinuation, if applicable) must be recorded on the AE CRF page and reported to the CRO and Revance according to the reporting procedures outlined in Section 6.3. This may include unresolved previously reported SAEs, or new SAEs. The Investigator should follow these SAEs until the events are resolved, or the subject is lost to follow-up. The Investigator should continue to report any significant follow-up information to the Medical Monitor, Revance and the IRB/IEC up to the point the event has been resolved. Resolution means the subject has returned to the baseline state of health, or the Investigator does not expect any further improvement or worsening of the subject's condition.

Any new SAEs reported by the subject to the Investigator that occur after the last scheduled contact and are determined by the Investigator to be reasonably associated with the administration of investigational product should be reported to Revance and the IRB/IEC.

7 STATISTICAL ANALYSIS

7.1 GENERAL CONSIDERATIONS

The analysis of data from the trial will be performed when all subjects have completed the trial or discontinued prematurely, and all data are in the database and have been cleaned and verified. All statistical programming will be performed using statistical analysis system (SAS) version 9.4 or higher.

A Statistical Analysis Plan, describing all statistical analyses, will be provided as a separate document prior to database lock and unblinding of the study treatments.

7.2 ANALYSIS POPULATIONS

All subjects who are randomized and receive treatment will be included in the Intent-to-Treat (ITT) population. The summaries will be by treatment as randomized.

All subjects who are randomized, receive treatment, and have provided at least one post-treatment safety assessment will be included in the safety population. The summaries will be by treatment actually received.

The Per-Protocol (PP) population will include subjects from the ITT population who complete the 4-week evaluation without a major protocol violation. [REDACTED]

[REDACTED]

- [REDACTED]
- [REDACTED]
- [REDACTED]
- [REDACTED]
- [REDACTED] ■ [REDACTED]

7.3 TRIAL ENDPOINTS

Unless specified otherwise, all endpoints associated with IGA-FWS, PFWS, GAIS, or Subject's Diary, henceforth will be based on assessments at maximum frown.

Primary Efficacy Endpoint:

The primary efficacy endpoint of the trial is the proportion of responders with the response defined as

- Achieving a score of 0 or 1 (none or mild) and an improvement of at least two points from baseline on both IGA-FWS and PFWS scales concurrently at Week 4

- █ [REDACTED]
- █ [REDACTED]
- █ [REDACTED]
- █ [REDACTED]
- █ [REDACTED]
- █ [REDACTED]
- █ [REDACTED]
- █ [REDACTED]
- █ [REDACTED]
- █ [REDACTED]

Safety Endpoints:

- Frequency, severity and relationship to study drug of treatment-emergent adverse events during the first four weeks post treatment and the overall study duration
- Frequency, severity and relationship to study drug of treatment-emergent serious adverse events during the first four weeks post treatment and the overall study duration

7.4 SUMMARIES OF TRIAL CONDUCT AND TREATMENT GROUP COMPARABILITY

The number of subjects randomized will be tabulated by trial center and treatment group. Subject disposition (the number of subjects randomized, treated, and completing each key trial visits) will be tabulated by treatment group. Premature study discontinuation and reasons for discontinuation will be summarized. Eligibility criteria deviations and other major protocol violations will be summarized.

Demographic and baseline characteristics will be summarized for all randomized subjects by treatment groups.

7.5 EFFICACY ANALYSES

Unless specified otherwise, the main method of handling missing efficacy data will be

[REDACTED]

[REDACTED]

See Section 7.5.5 for details on methods of handling missing data.

Descriptive statistics will be provided for all efficacy variables at all timepoints by treatment group. The point estimate of the treatment difference and 95% confidence interval (CI) of the difference (or 90% CI when the comparisons are 1-sided) will be generated.

7.5.1 PRIMARY EFFICACY ENDPOINT

Primary clinical efficacy will be assessed by the blinded evaluator who will grade the severity of the subject's glabellar lines at maximum frown using the IGA-FWS and the subject who will grade the severity of their glabellar lines at maximum frown using the PFWS. A response is defined as achieving a score of 0 or 1 (none or mild) and an improvement of at least two points from the baseline, on both the IGA-FWS and PFWS scales concurrently at the time point of evaluation. With both IGA-FWS and PFWS using a 4-point scale and the target population having a score of 2 or 3 (moderate or severe) at baseline, achieving an improvement of at least two points is inclusive in the status of achieving a score of 0 or 1 (none or mild). Henceforth, the response defined here will be abbreviated as "2-point composite response."

The proportion of subjects who have a 2-point composite response at Week 4 will be compared between daxibotulinumtoxinA and placebo using the Cochran–Mantel–Haenszel (CMH) test stratified by trial center using a two-sided test with a Type I error rate of 0.05.

[REDACTED]

[REDACTED]

[REDACTED]

[REDACTED]

[REDACTED]

[REDACTED]

[REDACTED]

[REDACTED]

- [REDACTED]
- [REDACTED]

[REDACTED]

[REDACTED]

[REDACTED]

- [REDACTED]
- [REDACTED]
- [REDACTED]

[REDACTED]

[REDACTED]

[REDACTED]

- [REDACTED]
- [REDACTED]

[REDACTED]

[REDACTED]

[REDACTED]

- | [REDACTED]
- | [REDACTED]
- | [REDACTED]

[REDACTED]

[REDACTED]

[REDACTED]

- | [REDACTED]
- | [REDACTED]
- | [REDACTED]

[REDACTED]

[REDACTED]

7.5.5 HANDLING MISSING DATA AND OTHER CONSIDERATIONS

Missing Data

[REDACTED]

[REDACTED] For endpoints that are a composite and/or derived from study assessments, imputation of missing data will be performed on the original assessments first.

No imputations will be utilized for the PP analyses.

As needed, a model-based multiple imputation approach may be explored to assess the impact of different imputation methods on the trial outcomes.

Pooling Data

Most of the efficacy endpoints are analyzed with trial center as a stratification factor. The trial is intended to be conducted in a manner such that a minimum of 5 ITT subjects in each treatment group will be enrolled at each trial center/site. In the event that there are too few subjects in a treatment arm at a single site, this site will be combined with another to achieve the desired minimum sample size per arm.

7.5.6 SENSITIVITY AND SUBGROUP ANALYSES

The robustness of main analysis results for the primary and secondary endpoints will be evaluated via sensitivity analyses on the per-protocol population and on data with missing values imputed using different approaches, such as no imputation (observed data only) or when necessary, multiple imputation.

Statistical tests will be conducted to identify if there are extreme trial centers that could affect the interpretation of common statistical and clinical conclusions. A CMH test of the primary efficacy endpoint will be conducted with factors of treatment group stratified by trial center. [REDACTED]

[REDACTED]

[REDACTED]

[REDACTED]

[REDACTED]

[REDACTED]

7.6 SAFETY ANALYSES

7.6.1 ADVERSE EVENTS

Safety summaries and analyses will be performed on the safety population. Descriptive statistics will be presented to summarize the safety data.

All AEs will be recorded and classified on the basis of MedDRA terminology. Treatment-emergent AEs are those AEs with an onset on or after the date and time of study treatment. All treatment-emergent AEs will be summarized by treatment group, system organ class, preferred term, severity, relationship, and seriousness.

Comparisons between treatment groups will be made by tabulating the frequency of subjects with one or more treatment-emergent AEs (classified into MedDRA terms) from baseline (post-treatment) to Week 4 as well as from baseline (post-treatment) through the duration of the trial.

Serious adverse events (SAEs) will be listed by subject. SAEs will be summarized by treatment group, severity, and relationship to study treatment. Each subject will be counted only once within a system organ class or a preferred term using the event with the greatest relationship and greatest severity.

All information pertaining to AEs noted during the trial will be listed by subject, detailing the verbatim description given by the Investigator, preferred term, system organ class, start date, stop date, severity, action taken regarding study drug, corrective treatment, outcome, and drug relatedness. The event onset will also be shown relative (in number of days) to the date of first study treatment administration. In addition, a list of subjects who prematurely discontinued from the trial due to adverse events will also be provided.

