3.1.1 DURATION OF TRIAL

The duration is up to 38 weeks on trial, including a screening period of up to two weeks followed by a single treatment and a follow-up period of up to 36 weeks post-treatment. All subjects will be followed for at least 24 weeks post-treatment.

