6 EVALUATION OF ADVERSE EVENTS

6.1 DEFINITIONS

For this protocol, an **adverse event (AE)** is any untoward medical occurrence (e.g., sign, symptom, disease, syndrome, intercurrent illness, clinically significant abnormal laboratory finding, injury or accident) that emerges or worsens following administration of investigational product and until the end of trial participation that may not necessarily have a causal relationship to the administration of the investigational product. An AE can therefore be any unfavorable and/or unintended sign (including a clinically significant abnormal laboratory result), symptom, or disease temporally associated with the use of an investigational product, whether or not considered related to the investigational product. A treatment-emergent AE is one that occurs after any period of exposure to treatment.

Pre-existing conditions, which increase in frequency or severity or a change in nature as a consequence of an investigational product use will also be considered an adverse event.

An unexpected AE is an adverse reaction, the nature or severity of which is not consistent with the applicable product information (e.g., Investigator's Brochure for an unapproved investigational product or package insert/summary of product characteristics for an approved product).

Any clinically significant change in the study safety evaluations, (e.g., vital signs, injection site evaluation, [REDACTED] [REDACTED]) post-treatment must be reported as an AE.

A **serious adverse event (SAE)** is any untoward medical occurrence that results in any of the following outcomes:

- Death
- Life-threatening, (i.e., the subject was, in the opinion of the Investigator, at immediate risk of death from the event as it occurred. It does not apply to an AE that hypothetically might have caused death if it were more severe)
- Persistent or significant disability/incapacity or substantial disruption of the subject's ability to carry out normal life functions
- Requires in-patient hospitalization or prolongs hospitalization (i.e., a prolonged hospitalization beyond the expected length of stay; hospitalizations for elective medical/surgical procedures, scheduled treatments, or routine check-ups are not SAEs by this criterion)
- Congenital anomaly/birth defect (i.e., an adverse outcome in a child or fetus of a subject exposed to the molecule or investigational product before conception or during pregnancy)

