2.1. Overall Study Design and Plan

This is a phase 3, double blind, placebo-controlled, multi-center trial to evaluate the efficacy and safety of a single intramuscular (IM) treatment of DaxibotulinumtoxinA for Injection for the temporary improvement in the appearance of glabellar lines in adults compared to a placebo.

The duration is up to 38 weeks on trial, including a screening period of up to two weeks followed by a single treatment and a follow-up period of up to 36 weeks post-treatment. All patients will be followed for at least 24 weeks post-treatment. Starting at Week 24 post-treatment, patients will be followed until their wrinkle severity in the glabellar lines at maximum frown returns to baseline in both the Investigator Global Assessment-Facial Wrinkle Severity (IGA-FWS) and Patient Facial Wrinkle Severity (PFWS) assessments.

[figure not shown]

Revance Therapeutics, Inc.

Confidential

Page 9 of 47

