3.3. Safety Assessments

3.3.1. Adverse Events

All adverse events (AEs) will be recorded and classified on the basis of MedDRA terminology. AE severity will be graded as mild, moderate, or severe as defined in Section 6.1.2 of the protocol. AEs with an onset on or after the date and time of study treatment will be Treatment-emergent.

The safety endpoints derived from the AEs are:

- Frequency, severity and relationship to study drug of treatment-emergent adverse events during the first four weeks post treatment and the overall study duration
- Frequency, severity and relationship to study drug of treatment-emergent serious adverse events during the first four weeks post treatment and the overall study duration

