4.8.1. Extent of Exposure

All patients receive one administration of investigational product. The sum of volume of investigational product injected and the volume of investigational product injected at each of the five injection sites will be summarized by treatment group using descriptive statistics (number of non-missing observations, mean, median, minimum, maximum, and standard deviation).

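### The whole-trial adverse event comparison runs over follow-up that can differ by arm, because from Week 24 a subject's exit depends on loss of effect; a fixed Week 24 window is needed

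*Protocol*

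**What the plan says.** **Length of follow-up.** Protocol 3.1.1 sets a minimum: "All subjects will be followed for at least 24 weeks post-treatment". The maximum is 36 weeks. SAP 2.1 gives the exit rule: "Starting at Week 24 post-treatment, patients will be followed until their wrinkle severity in the glabellar lines at maximum frown returns to baseline" on both scales. The Protocol synopsis and section 4.2.5 say the same, and 4.2.5 ties the rule to safety follow-up. The possible exit visits are therefore Weeks 24, 28, 32 and 36. The rule does not mention treatment group.

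**Collection of events.** Protocol 6.1 defines an adverse event as one that emerges or worsens "following administration of investigational product and until the end of trial participation", so the window closes at each subject's own exit.

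**Comparison of arms.** Protocol 7.6.1 makes the between-group comparison by "tabulating the frequency of subjects with one or more treatment-emergent AEs", over two windows: "from baseline (post-treatment) to Week 4 as well as from baseline (post-treatment) through the duration of the trial". Protocol 7.3 and SAP 3.3.1 name the same two windows as safety endpoints, for example "treatment-emergent adverse events during the first four weeks post treatment and the overall study duration", and repeat them for serious events. SAP 4.8.3 adds breakdowns by organ class, preferred term, severity, relationship and seriousness.

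**Exposure.** SAP 4.8.1 notes that "All patients receive one administration of investigational product" and then summarises injected volume. The visible text of either document gives no Week 24 window for adverse events, no person-time rate and no summary of follow-up time.

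**The concern.** A crude count of subjects with at least one event rises with time under observation. Here the time after Week 24 is an outcome of treatment: subjects whose lines are still improved are kept, and those back at baseline leave. If the product works beyond Week 24 in more subjects than placebo does, the active arm has more observation time after Week 24. It then accumulates more events even when the underlying rate is the same in both arms, and the tilt grows with duration of effect.

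At stake is how one of the two stated safety windows is read. A difference between arms in the whole-trial table would mix any drug effect on adverse events with the difference in follow-up, and the visible tables would not let a reader separate them.

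**Working it through.** The plan states no figure to reproduce. It gives no adverse event rate and no expected follow-up by arm, and the sample size text is redacted.

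**Inputs from the documents.** Minimum follow-up 24 weeks, maximum 36 weeks, exit visits at Weeks 24, 28, 32 and 36.

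**Assumptions, not in the documents.** The same constant hazard in both arms (no drug effect on events); all placebo subjects leave at Week 24; the 24-week risk p and the share s of active subjects followed beyond Week 24 are varied.

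**Formula.** The probability of at least one event by week t is P(t) = 1 − (1 − p)^(t/24). For p = 30%:

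- P(24) = 30.0%
- P(28) = 1 − 0.7^(28/24) = 34.0%
- P(32) = 1 − 0.7^(32/24) = 37.8%
- P(36) = 1 − 0.7^(36/24) = 41.4%

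With share s followed beyond Week 24, the spurious excess lies between s × (P(28) − p), if all of them leave at Week 28, and s × (P(36) − p), if all stay to Week 36:

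| s | all leave at Week 28 | all stay to Week 36 |
|---|---|---|
| 10% | 0.4 points | 1.1 points |
| 50% | 2.0 points | 5.7 points |
| 100% | 4.0 points | 11.4 points |

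Exits spread over the later visits fall between these limits. For s = 10% with mean active follow-up of 24.7 weeks, the active figure is 30.7%, an excess of 0.7 points; the formula at that mean gives 1 − 0.7^(24.7/24) = 30.7%. For s = 50% with a mean of 28.0 weeks, the active figure is 33.9%, an excess of 3.9 points.

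**Other rates.** From s = 10% (mean 24.7 weeks) to all active subjects at Week 36, the excess is 0.3 to 4.6 points at p = 10% and 0.9 to 14.6 points at p = 50%. For rare events the risk ratio approaches 36/24 = 1.5; at p = 2% with all active subjects to Week 36 it is (1 − 0.98^1.5)/0.02 = 1.49.

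**What shrinks it.** If 5% of placebo subjects also stay to Week 36, placebo shows 0.95 × 30% + 0.05 × 41.4% = 30.6%, and at p = 30% the excess falls to between 0.1 and 10.9 points. If all events start before Week 24, it is zero.

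**Check of remedies, with equal true risk.** A cut-off at Week 24 gives both arms P(24), so the difference is 0 and the risk ratio 1.00 at every rate. A person-time rate also gives 1.00 if the hazard is constant. If all events occur soon after injection, however, dividing by longer active follow-up gives a rate ratio of 24/28 = 0.86 at 28 weeks' mean active follow-up, and 24/36 = 0.67 if all active subjects stay to Week 36.

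**The case against.** The strongest reply has five parts.

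- **The rule is common to both arms.** A reader might infer separate schedules, with placebo released at Week 24 and active kept to Week 36. The documents do not say that. An active subject back at baseline on both scales leaves at Week 24, and a placebo subject still off baseline on either scale stays. This stands. The imbalance is conditional on duration of effect, for which the visible text gives no figure.
- **Little may happen after Week 24.** After a single injection a constant hazard suits background events better than treatment-related ones, and an equal-window comparison to Week 4 is already planned. This stands for early events. It does not cover later ones, and the plan cannot assume there are none.
- **The analysis is descriptive.** No visible test on adverse events would be invalidated, tables by relationship help interpretation, listings show onset day, and the tilt runs against the active product. All true, but Protocol 7.6.1 calls this table the comparison between groups, and a listing does not correct a table.
- **Follow-up is partly reported.** Protocol 7.4 and SAP 4.2 tabulate completion of key visits by treatment group. The visible text does not define which visits are key, so this helps only in part.
- **Some SAP text is not visible.** Section 3.3.2, parts of 4.8 and 4.9 and the table shells are not shown, so a further table there cannot be excluded. The statement of absence applies to the visible text.

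**Conclusion.** The concern holds as a conditional one. If the effect outlasts Week 24 in more active than placebo subjects, and early dropout does not offset this, the whole-trial comparison of subjects with at least one treatment-emergent or serious event is tilted against the active arm for events starting after Week 24. The Week 4 comparison and the primary efficacy endpoint are untouched.

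The size cannot be determined from the documents. At an assumed 24-week risk of 30%, with equal constant hazards and all placebo subjects out at Week 24, it runs from about 0.7 points to an upper bound of 11.4. It is near zero if events fall early or some placebo subjects also stay on. Under these assumptions the risk ratio cannot exceed 1.5.

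Two stronger readings are not supported. A reader might infer that a bias of several points is certain; nothing in the documents fixes either the event rate or the share of subjects who stay, and the upper bound needs every active subject to reach Week 36. A reader might also infer that the whole-trial table is unusable. It remains a valid description of what was observed in each arm, and events up to Week 24 within it are not affected by the exit rule. It should not be the main long-term comparison.

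**What to change.** - In Protocol 7.6.1 and SAP 4.8.3, make the main long-term comparison treatment-emergent and serious adverse events with onset through one fixed study day for Week 24. Bring the endpoint lists in Protocol 7.3 and SAP 3.3.1 into line.
- State that day under SAP 4.9.5, which renames Day 0 as Study Day 1. Counting seven days a week from Day 0, Week 24 is Day 24 × 7 = 168, or Study Day 169. Protocol Table 2 allows 3 days either side, so the visit can fall on Study Days 166 to 172. Study Day 166 is the latest cut-off that every subject with an in-window Week 24 visit has reached.
- Keep the whole-trial table as supportive, with onset after Week 24 shown separately by arm.
- Add a summary of follow-up time by arm to SAP 4.8.1.
- Use exposure-adjusted rates only as a supplement, noting that they over-correct in favour of the active arm for events clustered soon after injection.

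The cost is some wording and a few extra tables. Onset dates and visit dates are already collected, so no new data are needed.

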7.6.2 LABORATORY TESTS

Laboratory test results will be summarized with descriptive statistics for each treatment group at Screening and Final Evaluation Visit. Change from Screening to Final Evaluation Visit also will be summarized for continuous test results.

Shift tables will be presented to summarize laboratory test results at Screening and Final Evaluation Visit. Normal ranges established by the central laboratory will be used to

determine shifts. A listing of all out-of-range laboratory test results at any evaluation will also be provided. Determination of clinical significance for all out-of-range laboratory values will be made by each investigator and included in the listing. In addition, a listing of all clinically significant laboratory test results will be provided.

[REDACTED]

UPTs will be summarized for all treated subjects in the category of WOCBP by treatment group and presented in the data listings.

7.6.3 VITAL SIGNS AND PHYSICAL EXAMINATION

Vital signs and abnormal findings from the physical examination will be summarized with descriptive statistics for each treatment group by visit.

